### **2.2.4. Exploratory Objectives**

The exploratory objectives are the following:

- To evaluate the persistence of the immune response of the BD of mRNA-1273 vaccine (50  $\mu$ g) as assessed by the level of SARS-CoV-2 S2P specific bAb through 1 year after BD
- To evaluate the persistence of the immune response of the BD of mRNA-1273 vaccine (50  $\mu$ g) as assessed by the level of nAb through 1 year after BD
- To evaluate the incidence of SARS-CoV-2 infection or COVID-19 after vaccination with mRNA-1273

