#### **4.3.4. Part 3**

With at least 300 adolescents enrolled in Part 3 to receive 50 µg mRNA-1273.222, the study will have at least a 95% probability to observe at least 1 participant with an AE at a true AE rate of 1%.

Assuming a true serum Ab GMR of 1.6 for GM value against Omicron BA.4/BA.5 at Day 29 after Dose 1 of mRNA 1273.222 in baseline SARS-CoV-2 positive adolescents compared with GM value against Omicron BA.4/BA.5 at Day 57 after Dose 2 of mRNA-1273 primary series in young adults who are baseline SARS-CoV-2 negative in P301, with approximately 168 participants in the PP immunogenicity subset who are baseline SARS-CoV-2 positive in P203 Part 3 and 300 young adults in P301 who are baseline SARS-CoV-2 negative, there will be at least >90% power to demonstrate superiority of the serum Ab GM value against Omicron BA.4/BA.5 after Dose 1 of mRNA-1273.222 in adolescents in P203 to that after Dose 2 of mRNA-1273 in young adults in Study P301 at two-sided  $\alpha$  of 0.05 using a superiority margin of 1.0. The standard deviation of the natural log transformed levels of Ab is assumed to be 1.5.

Assuming a true serum Ab GMR of 1.1 for GM value against ancestral strain at Day 29 after Dose 1 of mRNA 1273.222 in baseline SARS-CoV-2 positive adolescents compared with GM value against ancestral strain at Day 57 after Dose 2 of mRNA-1273 primary

series in young adults who are baseline SARS-CoV-2 negative in P301, this sample size will also provide at least >90% power to demonstrate noninferiority of GM value of Ab against ancestral strain at Day 29 post Dose 1 of mRNA-1273.222 in adolescents in P203 to that after Dose 2 of mRNA-1273 in young adults in Study P301 at two-sided  $\alpha$  of 0.05 using a noninferiority margin of 1.5. The standard deviation of the natural log transformed levels of Ab is assumed to be 1.5.

With approximately 30% of participants in Part 3 who may be excluded from the PP Immunogenicity Subset-baseline SARS-CoV-2 positive (PPIS-POS), as they may be baseline SARS-CoV-2 negative or have missing immunogenicity results due to any reason or protocol deviations impacting critical data, approximately 240 participants are required in Part 3 to provide 168 participants in the PP Immunogenicity Subset-baseline SARS-CoV-2 positive.

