**5.3. Per-protocol (PP) Immunogenicity Subset**

**Per-protocol (PP) Immunogenicity Subset (Long-term Analysis at Day 1, Day 57 and Day 209)**

Per-Protocol (PP) Immunogenicity Subset (Long-term Analysis) consists of all participants in Immunogenicity Subset (Long-term Analysis) who meet all the following criteria:

- a) Received planned doses of study vaccination per schedule
- b) Complied with the timing of second dose of injection
- c) Had a negative SARS-CoV-2 status at baseline (pre-dose 1)
- d) Had no major protocol deviations that impact key or critical data

The PP Immunogenicity Subset (Long-term Analysis) will serve as the population for the long-term analysis of immunogenicity data.

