### Analysis periods

The following analysis periods and treatment groups will be used for Long-term Analysis (including Part 1B) and Part 1C-1 Homologous Booster Dose Analysis.

- Long-term Analysis (Part 1A plus Part 1B)

Cohort	Category	Start Date	End Date
mRNA-1273	Safety	Date of First Dose of mRNA-1273	Earliest date of booster dose, study discontinuation, study completion, death, or data cutoff
Placebo - mRNA-1273			
mRNA-1273	Efficacy/ Immunogenicity	Date of First Dose of mRNA-1273	Earliest date of booster dose (inclusive), study discontinuation, study completion, death, or data cutoff
Placebo - mRNA-1273			

Long-term analysis of incidence rate will also be performed for the entire study period after the first dose of mRNA-1273 regardless of booster dose.

- Part 1C-1 Homologous Booster Dose Analysis

Cohort	Category	Start	End
mRNA-1273 - Booster	Safety	Date of Booster Dose	Earliest date of study discontinuation, study completion, death, or data cutoff
Placebo - mRNA-1273 - Booster			

mRNA-1273 - Booster	Efficacy/ Immunogenicity	Date of Booster Dose (considered as pre- booster data)	Earliest date of study discontinuation, study completion, death, or data cutoff
Placebo - mRNA-1273 - Booster			

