To characterize the immunogenicity of mRNA-1273 in SARS-CoV-2 Ab including durability of immune-response (e.g. in the long-term analysis at Day 57 and Day 209), an exploratory analysis using a mixed model for repeated measures (MMRM) may be conducted. If performed, this analysis will be based on the participants receiving mRNA-1273 in the Per-protocol (PP) Immunogenicity Subset with negative baseline SARS-CoV-2 status.

For each select SARS-CoV-2-specific nAb and S protein-specific bAb of interest, the model will include all available log-transformed antibody titers at each post-Dose 1 of mRNA-1273 timepoints as the dependent variable. No treatment group variable in the model as all subjects in the model have received primary series of mRNA-1273. The model will include Visit (as a class variable, e.g. Day 57, Day 209) as fixed effects, and subject as a random effect. The model may also adjust for other covariates such as age groups and sex. An unstructured covariance structure will be used to model the within-subject errors. A Kenward-Roger approximation will be used for the denominator degrees of freedom. If there is a convergence issue due to the unstructured covariance matrix, a

compound symmetry covariance structure will be used to model the within-subject errors. No imputation of missing data will be done.

GMT at each post-Dose 1 timepoint will be estimated by the geometric least squares mean (GLSM) and corresponding 2-sided 95% CI estimated from the model. Ratio of GMT (fold change) between specified two timepoints will be estimated by the ratio of GLSM. For example, fold change from Day 57 to Day 209 could be estimated by the ratio of GLSM from the model. The corresponding 95% CI results in log-transformed scale estimated from the model will be back-transformed to obtain these estimates in the original scale.

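### Persistence titers in baseline-negative participants are not stopped at a SARS-CoV-2 infection after dosing, so waning tends to be understated

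*SAP*

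**What the plan says.** **Objectives.** Section 2.2 of the Part 1A SAP makes persistence of binding and neutralizing antibody over the year after dose 2 a secondary objective. Its section 3.2 sets GMs at Day 209 and Day 394, and section 6.4.4 summarizes titers at every sampling time. In the SAP for the other parts, persistence is exploratory. For the homologous booster it is to be evaluated "as assessed by the level of nAb through 1 year after BD" (section 2.2.4), with visits at BD-Day 181 and BD-Day 361 (section 3.2.4).

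**Populations.** The Part 1A PP Immunogenicity Subset (section 5.4) tests for infection at baseline only. The long-term PP subset (section 5.3 of the other SAP) has one infection criterion: "Had a negative SARS-CoV-2 status at baseline (pre-dose 1".

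**Durability model.** Section 6.4.6 says that "an exploratory analysis using a mixed model for repeated measures (MMRM) may be conducted". The participants are those in the "Per-protocol (PP) Immunogenicity Subset with negative baseline SARS-CoV-2 status", and "the model will include all available log-transformed antibody titers at each post-Dose 1 of mRNA-1273 timepoints as the dependent variable".

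**When titers stop counting.** Section 6.1 ends the long-term immunogenicity period at the "Earliest date of booster dose (inclusive), study discontinuation, study completion, death, or data cutoff" and the Part 1C-1 period at the "Earliest date of study discontinuation, study completion, death, or data cutoff". The Part 1A period ends at unblinding, non-study COVID-19 vaccination, crossover, booster, discontinuation, completion, death or cutoff. Infection is in none of the three lists.

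**Where later infection is handled.** Section 5.3 defines a Part 1C-1 set with no evidence of infection up to BD-Day 1, used for the primary and key secondary analyses. The wider Part 1C-1 PP subset is analyzed by pre-booster status (sections 5.3 and 6.4).

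**The concern.** The stated aim is persistence of the response to the vaccine or booster. A participant who is negative at baseline and infected six months later contributes a titer that reflects both exposures. The share of such participants can only grow with follow-up, so the distortion is largest at the late visits, where persistence is read.

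The SAP applies the opposite logic elsewhere. The Part 1A period stops titers at non-study COVID-19 vaccination, which is another immunizing exposure. The Part 1C-1 primary analysis screens out participants infected before the booster. The same sample of about 400 booster recipients supplies the long-term Day 57 and Day 209 titers (section 6.4.1), but there the PP set looks only at status before dose 1.

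At stake are the late GMs, fold rises and seroresponse rates, and the Day 209/Day 57 ratio from the model. All would tend to show a slower decline than vaccination alone produces.

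**Working it through.** The plan states no figure to reproduce here. The check is a comparison of rules followed by a bias calculation.

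**1. Is there a stopping rule?**

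| Summary | Infection status required | Stopped at later infection? |
|---|---|---|
| Part 1A GMs, Day 209 and Day 394 | negative at baseline | no |
| Long-term PP subset | negative before dose 1 | no |
| Durability model | negative at baseline | no |
| Part 1C-1 paired Day 209 vs Day 57 | reported by pre-booster status | not stopped, but infections detected by BD-Day 1 are separated |
| Part 1C-1 BD-Day 181 and BD-Day 361 | negative before the booster, or split by that status | no |

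The fourth row matters. In the mRNA-1273 arm BD-Day 1 is nominally Day 209 (Appendix G of the Part 1A SAP), and the tested sample consists of booster recipients. Pre-booster negatives therefore give a Day 209/Day 57 ratio without detected infection up to the booster.

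**2. Size of the bias.** Let p be the share of titers at a visit that follow an infection, and F the geometric mean factor by which infection has raised them above their uninfected level. Then

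mean log titer = log GM(uninfected) + p × log F, so GM(observed) = GM(uninfected) × F^p.

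For a ratio of two visits, p is in effect the share newly infected between them. The SAP gives neither p nor F, so both are assumed:

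| | p = 5% | p = 10% | p = 25% |
|---|---|---|---|
| F = 2 | 1.04 | 1.07 | 1.19 |
| F = 4 | 1.07 | 1.15 | 1.41 |
| F = 10 | 1.12 | 1.26 | 1.78 |

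The smallest entry is 2^0.05 = 1.035 and the largest is 10^0.25 = 1.778. If the infection-free Day 209/Day 57 ratio were 0.50 (assumed), the observed ratio would run from 0.50 × 1.035 = 0.52 to 0.50 × 1.778 = 0.89.

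**3. What anchors p?** Only loosely, the planned exclusion of about 25% in section 6.4.1. It combines pre-booster positivity with missing results, so it is a loose upper guide to infection before the booster. It does not bound infection afterwards.

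**4. Calendar.** Boosters in the sampled subset start on 27 Dec 2021. Adding 180 and 360 days puts BD-Day 181 at 25 Jun 2022 or later and BD-Day 361 at 22 Dec 2022 or later. Sections 4.1.1.4 and 4.1.2 of the Part 1A SAP cite the emergence of Omicron as the reason for stopping enrollment on 16 August 2022. This makes infection between those visits plausible, but it does not measure p.

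**The case against.** **All-titer GMs are a legitimate target.** Observed titers regardless of infection answer a treatment-policy question, and the objectives are framed as antibody levels. This stands as a reason to keep that summary. It does not excuse leaving the target unstated when the objective concerns the response to the vaccine.

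**Dropping post-infection titers has its own bias.** If low titers raise infection risk, those who remain have higher titers and durability can again be overstated. This stands. The repeated-measures model can use Day 57 titers to offset part of it if the remaining data are missing at random; visit-by-visit GMs cannot. It is why the restricted summary belongs beside the all-titer one and should not replace it.

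**The stakes are modest.** The model is optional and exploratory, no success criterion attaches to any persistence summary, and Part 1A titers are already cut at unblinding, crossover or booster. The sampling plan lists testing at Day 1, Day 57, Day 209, BD-Day 1 and BD-Day 29, so BD-Day 181 and BD-Day 361 may not be tested at all. This stands; the Part 1A GMs are nevertheless secondary and share the gap.

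**Stronger readings that the documents do not support.**
- A reader might infer that infection after dosing is never dealt with. The Part 1C-1 analyses by pre-booster status contradict that for Day 209 against Day 57.
- A reader might tie the bias to Delta. The SAP names only Omicron.
- A reader might take p to be large because "approximately 240 participants are required in Part 3 to provide 168 participants in the PP Immunogenicity Subset-baseline SARS-CoV-2 positive". That 168/240 = 70% is a planning figure for status before the first Part 3 dose, not infection after dosing in the persistence cohorts.
- A reader might extend the point to Parts 2 and 3. Their main immunogenicity sets are baseline-positive, so titers already reflect infection. Nucleocapsid conversion also cannot be seen in someone who is already seropositive.

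**Conclusion.** The point holds for the sets selected as negative at baseline or before the booster. The Part 1A GMs at Day 209 and Day 394, the long-term subset, the durability model and any tested BD-Day 181 and BD-Day 361 samples mix in titers raised by later infection. Provided that infection raises spike-binding and neutralizing titers (F above 1), the bias is toward slower apparent waning.

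Its size cannot be determined from the SAP. The range of 1.04 to 1.78 rests wholly on assumed p of 5% to 25% and F of 2 to 10. Part 1C-1 already offers a partial remedy for Day 209 against Day 57. It ends at the booster and is not written into the model or the Part 1A GMs.

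A reader might conclude that the persistence objectives go unanswered. That is too strong: the all-titer GMs describe antibody levels as they occurred. What is missing is a companion estimate of the response to vaccination without later infection.

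**What to change.** In section 6.4.4 of the Part 1A SAP and section 6.4.6 of the other SAP:

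1. Keep the all-titer summary and label it as regardless of infection.
2. Beside it, prespecify a version for baseline-negative participants (pre-booster-negative for visits after the booster). It drops each participant's titers from the first positive RT-PCR or nucleocapsid conversion after the reference dose. Name that dose. Counting from the first dose for the primary series leaves no gap after the baseline test; for post-booster visits the reference is the booster.
3. Report the number infected by each visit.
4. In the durability model, apply the same rule or restrict to pre-booster negatives.
5. State the limits: fewer late titers, undetected infections remaining in, and possible selection if infection risk depends on titer, with a comment on the missing-at-random assumption.
6. Do not carry the nucleocapsid rule into the baseline-positive sets of Parts 2 and 3.

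The cost is some SAP wording, one derived flag and a second set of tables. Section 6.5 of both SAPs already summarizes RT-PCR and nucleocapsid serology by visit, so no new data are needed.

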##### Sampling Plan

The first ~400 participants in the mRNA-1273 group who received booster dose (third dose, starting from 27Dec2021) in Part 1C-1 and meet all the criteria below will be selected for the immunogenicity subset.

- The participant is in Full Analysis Set (Part 1C-1, Homologous Booster Dose).
- SARS-CoV-2 status is not missing for baseline (pre-dose 1).

The blood samples of these subjects collected at the long-term timepoints (Day 1, Day 57, and Day 209) and subsequent booster dose phase timepoints (BD-Day 1 and BD-Day 29) will have immunogenicity testing, to support both the long-term immunogenicity analysis and booster dose immunogenicity analysis.

The target is to obtain 289 participants in the PP Immunogenicity Subset with pre-booster negative SAR-CoV-2 status (adjusting for approximately 25% of participants who may be excluded as they may have pre-booster positive SAR-CoV-2 status, or have no immunogenicity results due to any reason).

For the noninferiority tests of Ab GM and seroresponse rate at BD-Day 29 in adolescents in Study P203 compared with the primary series GM at Day 57 in young adults (18-25 years of age) in Study P301 receiving mRNA-1273, an immunogenicity subset of 340 young adults in Study P301 randomly selected from all participants (18-25 years of age) receiving mRNA-1273 will be used, with a target of 289 participants in the PP Immunogenicity Subset (using same definition as in Study P203) after adjusting for

approximately 15% of participants not meeting inclusion criteria for PP Immunogenicity Subset.

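### The durability MMRM combines a random subject effect with an unstructured within-subject covariance, so one covariance parameter is redundant in both the model and its fallback

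*SAP*

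**What the plan says.** Section 6.4.6 of the SAP for Parts 1B, 1C, 2 and 3 describes the durability model in a single paragraph. "The model will include Visit (as a class variable, e.g. Day 57, Day 209") enters "as fixed effects, and subject as a random effect". The same paragraph adds: "An unstructured covariance structure will be used to model the within-subject errors". It also says: "A Kenward-Roger approximation will be used for the denominator degrees of freedom".

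The fallback reads: "If there is a convergence issue due to the unstructured covariance matrix, a" "compound symmetry covariance structure will be used to model the within-subject errors". Neither step removes the random subject effect, and nothing says that the phrase is meant only to name subject as the grouping unit of the repeated structure.

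On status, the section says that "an exploratory analysis using a mixed model for repeated measures (MMRM) may be conducted".

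**The concern.** An unstructured matrix gives every visit its own variance and every pair of visits its own covariance. The association that a random subject intercept would represent is therefore already in it. Fitting both asks the data to split one quantity into two parts that cannot be told apart. The likelihood is then flat along one direction and the information matrix for the covariance parameters is singular.

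Software may handle this quietly, or it may report non-convergence or a Hessian that is not positive definite. The Kenward-Roger adjustment also draws on that information matrix, so the redundancy can surface there too. If a failure is reported, the plan's only prescribed response is to replace the unstructured matrix, although the unstructured matrix alone would be identified. Compound symmetry then forces equal variance at the peak and after waning, and the per-visit confidence intervals would be misstated if the variances differ.

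**Working it through.** The SAP gives no numerical figure for this model, so there is nothing to reproduce. The check has two parts: what is identified, and what an unnecessary switch would cost.

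**1. Counting parameters.** The marginal covariance of one subject's T visits is V = s_b² J + R, where J is the all-ones matrix, s_b² is the random-intercept variance and R is the within-subject error covariance. V has T(T+1)/2 distinct elements. The number of identifiable parameters is the rank of the map from the parameters to those elements.

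| Visits T | Intercept + unstructured: parameters / rank | Unstructured alone: parameters / rank | Intercept + compound symmetry: parameters / rank |
|---|---|---|---|
| 2 | 4 / 3 | 3 / 3 | 3 / 2 |
| 3 | 7 / 6 | 6 / 6 | 3 / 2 |
| 4 | 11 / 10 | 10 / 10 | 3 / 2 |
| 5 | 16 / 15 | 15 / 15 | 3 / 2 |

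There is always exactly one parameter too many, in the main model and in the fallback. T = 2 corresponds to the SAP's own example of Day 57 and Day 209.

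**2. Numerical confirmation.** Complete two-visit data were simulated with n = 289, assumed log-scale SDs of 1.0 and 1.5 and an assumed correlation of 0.5. The 289 is borrowed for illustration from Section 6.4.1 (Sampling Plan): "The target is to obtain 289 participants in the PP Immunogenicity Subset with pre-booster negative SAR-CoV-2 status". With R set to S − s_b² J, where S is the sample covariance, −2 REML was 652.4485 at s_b² = 0, 0.1, 0.3, 0.5 and 0.7. R was positive definite in each case. One eigenvalue of the Hessian was about 6 × 10⁻⁸, against 104 to 1203 for the other three. That is an exact flat ridge. It shows non-identifiability. It does not show that a fit would fail.

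**3. Cost of moving to compound symmetry with complete pairs.** Let r be the ratio of the larger to the smaller visit SD, with the smaller set to 1. Compound symmetry uses the pooled SD, √((1 + r²)/2), at both visits. Relative to the unstructured model, the SE at the low-variance visit is multiplied by √((1 + r²)/2), and at the other visit by that value divided by r. At about this sample size, CI widths on the log scale follow the SEs closely.

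- r = 1.25: √(2.5625/2) = 1.13, and 1.13/1.25 = 0.91
- r = 1.5: √(3.25/2) = 1.27, and 1.27/1.5 = 0.85
- r = 2: √(5/2) = 1.58, and 1.58/2 = 0.79

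The ratios r are assumptions, because the SAP gives no visit-specific SDs.

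**4. Fold change.** With complete pairs, the variance of the difference is (v₁ + v₂ − 2c)/n under the unstructured model, where v₁ and v₂ are the visit variances and c their covariance. Under compound symmetry it is 2((v₁ + v₂)/2 − c)/n, which is the same. In the simulated data both SEs were 0.0764.

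**The case against.** The best defence has four parts.

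- **A converged fit does no harm.** Only the split between s_b² and R is unidentified. The marginal covariance stays fully general, and software may set s_b² to zero and proceed. This stands. A reader might infer that the model is misspecified or that its GMTs and CIs would be wrong. The documents do not support that: a converged fit gives the same marginal covariance, visit GMTs, CIs and fold change as the unstructured model alone. The model is over-parameterised, which is a lesser fault.
- **The fallback is limited to failures caused by the unstructured matrix.** Read strictly, a failure caused by the redundant intercept does not meet that trigger. This stands in part. The plan gives no way to tell the two causes apart and no step that drops the intercept first, so a wrong attribution is possible. A reader might infer that the switch is likely; nothing here shows that.
- **The phrase may be shorthand for grouping by subject.** It may. The text does not say so, and a programmer who follows it literally would code both terms.
- **The same quantities are reported elsewhere.** Section 6.4.6 also commits to GM levels at each time point with t-based CIs, which pool no variance across visits. For Part 1C-1 it commits to paired comparisons such as Day 209 against Day 57, where the same assay is available at both visits. This stands and limits the consequence considerably.

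**Conclusion.** The point holds as a minor specification error. As written, the model has one covariance parameter more than can be identified at any number of visits, and so does its fallback. That part is algebra and needs no assumption.

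The consequence is conditional. It needs a convergence or Hessian failure, attribution of that failure to the unstructured matrix, and visit SDs that differ. If all three occur, an assumed SD ratio of 1.5 makes the CI about 27% too wide at the low-variance visit and about 15% too narrow at the other. Over assumed ratios of 1.25 to 2 the range is 13% to 58% too wide and 9% to 21% too narrow. These figures illustrate what the switch would cost and are not evidence that it would happen. The fold change is unaffected with complete pairs.

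The analysis is optional and exploratory, and no primary or key secondary test depends on it.

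**What to change.** In the model sentence of Section 6.4.6, delete the clause that makes subject a random effect. Fit visit as a fixed effect with an unstructured within-subject covariance, and name subject as the grouping unit of that covariance.

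State that if this model itself fails to converge, the simpler structure is used, also without a random subject effect. Compound symmetry alone has 2 parameters and rank 2, so it is identified. Heterogeneous compound symmetry is a distinct option only with three or more visits: at two visits it has two variances and one correlation, which is the unstructured model again.

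The cost is one phrase in the SAP and a short addition to the fallback sentence. No data, sample size or other analysis changes.
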